## 5.2 EXCEPTIONS TO REPORTING

- 5.2.1 Grade 4 events related to AR-PCNSL or HIV and not to therapy will not require reporting. Examples include:
  - 5.2.1.1 Grade 4 lymphocytopenia
  - 5.2.1.2 Grade 4 CPK
  - 5.2.1.3 Grade 4 hyperuricemia
  - 5.2.1.4 Grade 4 hyperamylasemia without physiologic correlates of non-pancreatic origin.
  - 5.2.1.5 Since lymphocytopenia is a hallmark of HIV infection and this is highly likely in this population of patients, Adverse Event Reporting will not be required for any grade lymphocytopenia.
- 5.2.2 Grade 4 treatment-related events not requiring reporting:
  - 5.2.2.1 Leucopenia
  - 5.2.2.2 Neutropenia
  - 5.2.2.3 Uncomplicated (no microbiologic confirmation of infection) treatment-related febrile neutropenia requiring hospitalization.
- 5.2.3 Unexpected drug toxicities will be reported to the FDA via MedWatch.

## 5.3 RESPONSE CRITERIA

Response criteria are based on published standards for phase II studies of supratentorial malignant glioma and a modification of the response assessment of aggressive non-Hodgkin's lymphoma by integrated international workshop criteria and fluorine-18 – fluorodeoxyglucose positron emission tomography, and an international workshop to standardize baseline evaluation and response criteria for primary CNS lymphoma. Cross-sectional measurements of tumors will be used to assess baseline and responses.

- 5.3.1 Complete Response - disappearance of all enhancing lesions on MRI of the brain, negative FDG-PET scan persisting for at least 4 weeks in patients who were off corticosteroids, negative CSF cytology and neurologically improved from baseline.
- 5.3.2 Complete Response Unconfirmed (CRu) – either a CRu, PR or SD by MRI criteria with a completely negative FDG-PET off steroids, and negative CSF cytology. If there is no evidence of progression while off steroids for 4 months, response will be reclassified as CR.
- 5.3.3 Partial Response
  - 5.3.3.1 A reduction of enhancing tumor volume by more than 50% maintained for at least 4 weeks, steroids stable or reduced, and neurologically stable or improved with positive FDG-PET, or

- 5.3.3.2 Normalization of MRI, negative FDG-PET, but with persistent disease by CSF cytology.
- 5.3.4 Progressive disease - an increase of tumor volume of more than 25% or occurrence of new lesions, or neurologically worse, steroids stable or increased.
- 5.3.5 Stable disease – not meeting the criteria for complete response, partial response, or progressive disease and with a positive FDG-PET
- 5.3.6 Treatment failure - progressive or stable disease, relapse after initial response, death, or discontinuation of chemotherapy because of complications or because of patient's or Investigator's decision. Patients who require radiotherapy will be considered treatment failures for purposes of the protocol, regardless of long-term outcome.
- 5.3.7 Substantial brain dysfunction and cognitive problems (as referred to in sections 1.2.3 and 7.4.4) that will define treatment failure refer to post-treatment recurrent brain lymphoma, treatment related functional brain pathology, and/or neurologic function class 3 or 4 as defined in Appendix 2: Neurological Function Class.

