#### 2.1.2 Exclusion Criteria

2.1.2.1 Prior therapy for CNS lymphoma

2.1.2.1.1 Steroids not an exclusion

2.1.2.2 Evidence of lymphoma outside of the central nervous system

2.1.2.2.1 Ocular involvement will not exclude

2.1.2.3 Multidrug resistant HIV not amenable to long-term suppression based on either or both:

2.1.2.3.1 Clinical history of poor adherence to multiple antiretroviral drugs deemed sufficient to render effective HIV control unattainable;

2.1.2.3.2 HIV mutational analysis (genotyping and/or phenotyping) that reveals high-level resistance such that a combination regimen comprised of agents from at least two drug classes cannot be devised to suppress HIV long-term.

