3.8.2.1.6 Ophthalmologic examination to assess for ocular involvement by lymphoma

3.8.2.1.7 Viral hepatitis studies (not necessary to repeat previously documented positive studies; results not required prior to treatment):

- Hepatitis A
- anti-HAV IgG
- Hepatitis B
- anti-HBsAg
- HBsAg
- Anti-HB core
- Hepatitis C
- anti-HCV

- 3.8.2.1.8 Serum anti-toxoplasmosis antibody titers (not necessary to repeat if already obtained on NIAID protocol)
- 3.8.2.1.9 Syphilis serology (not necessary to repeat if already available within 6 months prior to study entry)
- 3.8.2.1.10 HIV viral load if not available within 14 days prior to enrollment
- 3.8.2.1.11 T-cell subsets if not available within 14 days prior to enrollment
- 3.8.2.1.12 HIV genotype or Virtual Phenotype® to assess for resistant HIV if not previously done
- 3.8.3 Day 1 each cycle; then monthly for 2 months, then every 2 months x3, then every 3 months x6, then every 6 months x 2, then every 12 months x 2 (for patients co-enrolled in 01-C-0038 and followed clinically beyond year 3).

For “Radiation-Sparing Best Available Care” Cohort, scheduled evaluations on Days 1, 8, 15, 21, 28 then monthly for 2 months, then every 2 months for 3 times, then every 3 months of total of 36 months, then yearly for 2 years (for patients followed clinically beyond year 3).

- 3.8.3.1 Physical examination with documentation of abnormalities
- 3.8.3.2 Particular emphasis on neurological examination
- 3.8.3.3 Assign neurologic function class (see [Appendix 2](#))
- 3.8.3.4 CBC with differential (CBC with differential drawn up to 24 hours prior to starting therapy acceptable for patients receiving filgrastim to manage neutropenia)
- 3.8.3.5 Electrolytes
- 3.8.3.5.1 Serum creatinine
  - calculated and/or measured creatinine clearance
  - Whenever the calculated creatinine clearance is <100 mL/min, a measured creatinine clearance should be obtained.
- 3.8.3.5.2 Hepatic panel
- 3.8.3.5.3 Mineral panel
- 3.8.3.6 During treatment cycles until serum methotrexate level  $\leq 0.05$  mcmol/L:
  - 3.8.3.6.1 Blood specimens for methotrexate levels must be drawn at scheduled times
  - 3.8.3.6.2 Hepatic panel every other day
  - 3.8.3.6.3 CBC with differential daily
  - 3.8.3.6.4 Electrolytes, creatinine, BUN daily
- 3.8.4 Baseline Staging
- 3.8.4.1 MRI: if done within 2 weeks before study entry, repeat only if interval clinical deterioration has occurred

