- 3.8.4.2 FDG-PET: not necessary to repeat if previously done within 3 weeks of study entry
- 3.8.5 Restaging
- 3.8.5.1 MRI
  - 3.8.5.1.1 End of cycles 2, 4, 6 and 8, then every 2 months x3, then every 3 months x 6, then every 6 months x 2, then as clinically indicated, or annually up to year 5

(for patients followed clinically beyond year 3). For “Radiation-Sparing Best Available Care” Cohort, Scheduled evaluations on Week 4, Week 8, Week 12, then every 2 months x3, then every 3 months x 5, then every 6 months x 2, then as clinically indicated, or annually up to year 5 (for patients followed clinically beyond year 3).

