### 3.8.5.2 Ophthalmologic

3.8.5.2.1 If ocular involvement, restage same schedule as with MRI

3.8.5.2.2 If no ocular involvement, examine for lymphoma if clinically indicated

### 3.8.5.3 FDG-PET

3.8.5.3.1 End of cycle 1

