### 11.3 APPENDIX 3: ON-STUDY EVALUATIONS

Cycle/ Visit	H&P	Ophtho Exam	Toxicity Assess	MMSE	Clin. Labs	Cr. Cl.	Screen	MRI	PET	CSF	HIV/ CD4	EBV	Research Blood	Neuro- psych	Adherence
Cycle 1	X		X	X	X	X		X 	X 	X 	X 	X	X		
Cycle 2	X		X	X	X	X		X							
Cycle 3	X		X	X	X	X		X							
Cycle 4	X		X	X	X	X		X							
Cycle 5	X		X	X	X	X		X							
Cycle 6	X		X	X	X	X		X							
Cycle 7	X		X	X	X	X		X							
Cycle 8	X		X	X	X	X		X							
CR by MRI		X 						X							
End Rx	X	X 	X	X	X	X		X							
Follow-up															
Q2 mo x3															
Month 2	X		X		X	X		X							
Month 4	X		X		X	X		X							
Month 6	X		X		X	X		X							
Q3 mo x6															
Month 9	X		X		X	X		X							
Month 12	X		X		X	X		X							
Month 15	X		X		X	X		X							
Month 18	X		X		X	X		X							
Month 21	X		X		X	X		X							
Month 24	X		X		X	X		X							
Q6 mo x2															
Month 30	X			X			X		X						
Month 36	X			X			X		X						
Q12 mo x2 (Optional Clinical Follow up)															
Month 48	X			X						X					
Month 60	X			X						X					

1. Repeat if abnormal at baseline.

H&P= History and Physical, including ECOG; Ophtho Exam = Ophthalmology exam for orbital involvement; Clin. Labs = CBC with differential and Retic, Chem. 20, PT/PTT, Urine: UA,  $\beta$ -hCG (women); Cr. Cl. = estimated creatinine clearance by Cockcroft-Gault formula (Appendix 4); Serology = Hepatitis and Toxoplasmosis serologies, RPR; CSF = CSF cell count, glucose, protein, EBV, molecular pathology, flow cytometry ; HIV/CD4 = Baseline HIV Serology, genotype if indicated, HIV viral load, and lymphocyte subset TBNK; EBV = EBV quantitative PCR, blood; Neuropsych, See Appendix 5; Adherence, see Appendix 6. BL = Baseline Studies; End Rx = End of therapy, Cycle 8, Day 28 (Month 1 follow-up).  
 For patients that relapse, re-staging will include: MRI-brain with contrast, CNS FDG-PET, CSF studies, quantitative EBV-PCR, and ophthalmologic examination. See Section 3.8.5.

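### Complete response in section 5.3 never uses the eye examination, so known ocular lymphoma that persists can be scored as CR

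*Combined protocol and SAP*

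**What the plan says.** The protocol treats the eye as a possible disease site from entry onwards.

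- Eligibility (2.1.2.2.1): lymphoma outside the central nervous system excludes a patient, but "Ocular involvement will not exclude".
- Baseline (3.8.2.1.6): "Ophthalmologic examination to assess for ocular involvement by lymphoma".
- Restaging (3.8.5.2.1): "If ocular involvement, restage same schedule as with MRI". The MRI schedule in 3.8.5.1.1 is "End of cycles 2, 4, 6 and 8, then every 2 months x3, then every 3 months x 6", with further visits after that.
- Appendix 3, main cohort: the eye examination carries the footnote "Repeat if abnormal at baseline".

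The response categories do not use the result.

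- CR (5.3.1): "disappearance of all enhancing lesions on MRI of the brain, negative FDG-PET scan persisting for at least 4 weeks" off corticosteroids, with "negative CSF cytology and neurologically improved from baseline".
- Unconfirmed CR, CRu (5.3.2): "either a CRu, PR or SD by MRI criteria with a completely negative FDG-PET off steroids, and negative CSF cytology". It becomes CR after four months off steroids without progression.
- PR (5.3.3.2): a normal MRI and negative PET with disease still present on CSF cytology is only PR. There is no matching clause for the eye.

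CR status is used in three places. Without CR by the end of cycle 6, a patient is a treatment failure (3.2). Only complete responders go on to cycles 7 and 8 (1.2.4.3, 3.2). The CR rate is a secondary objective (1.1.2.2), and section 6.1.3 says that all secondary endpoints are reported as exploratory.

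**The concern.** An examination is ordered to find and follow lymphoma at one site, but no rule says what its result does to the response category. If the eye is still involved when everything else has cleared, the written definitions give the most favourable category to a patient with residual lymphoma. The protocol takes the opposite line for CSF, where residual disease blocks CR.

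Two outcomes are at stake: the CR rate, which would be biased upward, and the end-of-cycle-6 failure classification, which such a patient would avoid. The primary outcome is also worded around recurrence (1.1.1.1, 6.1.3; brain recurrence in 5.3.7), and disease that never cleared is not plainly a recurrence. How far the primary fraction is exposed depends on other rules, traced below.

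**Working it through.** **1. The plan's own figure.** Section 6.1.3 gives n = 15, a one-sided exact binomial test at 0.10, 30% against 65%, and 88% power. With X ~ Bin(15, p), the rejection rule is the smallest r with P(X ≥ r | p = 0.30) ≤ 0.10.

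- r = 7: P(X ≥ 7 | 0.30) = 0.131, above 0.10.
- r = 8: P(X ≥ 8 | 0.30) = 0.050, within 0.10.
- Power at r = 8: P(X ≥ 8 | 0.65) = 0.887.

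The stated 88% is reproduced, and this point does not alter it.

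**2. Which category fits?** Take a patient with ocular lymphoma at baseline who has a cleared brain MRI, PET negative for at least four weeks off steroids, negative CSF cytology, neurological improvement, and unchanged ocular lymphoma on the restaging examination.

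| Category | What it needs | Met? |
|---|---|---|
| CR (5.3.1) | MRI, PET, CSF, neurological improvement | Yes, every element |
| PR (5.3.3.1) | Tumour volume reduction with a positive PET | No, PET is negative |
| PR (5.3.3.2) | Residual disease on CSF cytology | No, CSF is negative |
| Stable disease (5.3.5) | None of the other categories, and a positive PET | No |
| Progression (5.3.4) | Growth, new lesions or neurological worsening | No, the eye disease is known and unchanged |

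CR is the final category. If the MRI had not fully cleared, CRu would apply on PET and CSF alone, and it would convert to CR after four months without progression. Had the residual disease been in the CSF instead of the eye, the same patient would be PR.

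**3. Effect on the CR rate.** The shift is k/15 for k affected patients, if all 15 are in the denominator:

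- k = 1: 1/15 = 6.7 points
- k = 2: 2/15 = 13.3 points
- k = 3: 3/15 = 20.0 points

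These are shifts for a given k. The documents give neither the frequency of ocular involvement nor the frequency of ocular persistence after the brain clears, so k cannot be estimated.

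**4. Path to the primary fraction.** For the same patient to be a false success at two years, all of these must hold:

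- the ocular lymphoma persists but receives no radiotherapy or other additional lymphoma therapy, because 3.10.1 scores any such therapy as failure (5.3.6 and 3.7 repeat this for radiotherapy);
- the patient is alive at two years;
- there is no brain recurrence and no treatment-related functional brain pathology (5.3.7);
- Neurological Function Class is not 3 or 4 (5.3.7).

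If all hold, that patient moves the primary fraction by 6.7 points. Only if the count otherwise stood at 7/15 (p = 0.131) would the change to 8/15 (p = 0.050) cross the 0.10 level.

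**The case against.** The strongest reply is that the consequences are limited, and much of that stands.

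- **Primary outcome.** A reader might infer that residual ocular lymphoma is routinely counted as recurrence-free at two years. Section 3.10.1 does not allow that: once the eye disease needs further lymphoma therapy, the patient is a failure whatever the CR label. Only untreated persistence remains exposed.
- **Number affected.** A reader might assume an ocular rate of, say, 5% to 20% and conclude that 15 × 0.05 = 0.75 to 15 × 0.20 = 3 patients are misclassified. That range is an assumption, and it counts patients with ocular disease at entry. Misclassification also needs clearance everywhere else with persistence in the eye, so those figures are at most a ceiling.
- **Deciding the test.** The contrast between 7/15 and 8/15 holds for any single classification in a trial of 15. Section 6.1.3 also does not bind the decision to the test: it allows the strategy to go forward on less favourable results, weighed against other data.
- **Disease-free survival.** It is tempting to say that a false CR starts the disease-free interval. Section 1.1.2.2 lists disease-free survival, but the documents do not define its start.
- **Progression.** Section 5.3.4 does not limit new lesions by site, so a new ocular lesion could count. The firm gap is known ocular disease that persists, or worsens without neurological change.
- **Published criteria.** Section 5.3 says that its criteria are based on published standards. It then writes out its own definitions, and those are what will be applied.
- **Examination schedule.** Appendix 3 as available shows fewer eye examinations than 3.8.5.2.1, but its table is visibly broken, so nothing is built on the difference.

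None of this supplies a rule that keeps the step 2 patient out of CR. Leaving it to judgement is weak in a study expected to accrue over 6 to 10 years (6.1.3).

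**Conclusion.** The gap is real and goes beyond missing detail: applied as written, the rules give a definite and wrong classification. Known ocular lymphoma that persists after brain, PET and CSF clear is scored CR, contrary to the protocol's own handling of residual CSF disease.

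The size is 6.7 points on the CR rate per affected patient, assuming 15 in the denominator, always upward, together with avoidance of the end-of-cycle-6 failure classification. The CR rate is secondary and exploratory. The primary fraction is exposed by the same amount per patient only under the conditions in step 4, and the documents give no basis for saying how often they would be met. The sample size and power statement is unaffected. The documents do not support a claim that the primary result is generally biased.

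**What to change.** For outcome classification, reconcile section 5.3 with 3.8.5.2.1:

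- In 5.3.1 and 5.3.2, require no evidence of lymphoma on the scheduled eye examination for patients with ocular involvement at baseline.
- Class persistent ocular disease as less than CR, parallel to CSF disease in 5.3.3.2.
- State that persistent, new or worsening ocular lymphoma counts as lymphoma in the two-year outcome, and align the wording of 5.3.7 and 6.1.3 with this.

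The cost is small. For patients with baseline ocular disease the examinations are already required, so no visits are added. The downside is a slightly lower CR rate.

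One matter has to be kept apart. CR also determines who receives cycles 7 and 8 (1.2.4.3, 3.2), and section 3.2 ties failure status and the omission of those cycles together. A change in the CR definition would therefore reach treatment unless the two uses are separated. The sponsor should reconcile those sections and state any treatment consequence separately. This point recommends none.

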### 1.2.5 Novel Tumor Assessment and Psychometric Testing

In addition to the antitumor therapy, this protocol will in a preliminary manner assess novel measures of response and predictors of disease recurrence based on important recent advances in the diagnosis of AR-PCNSL. Based on the finding that essentially all AR-PCNSL are EBV associated, RT-PCR detection of EBV in the CSF has been found to be a sensitive and specific marker for lymphoma in HIV-infected patients with focal brain lesions. In combination with SPECT thallium or fluoro-2-deoxy-d-glucose positron emission tomography (FDG-PET) scanning of the brain, a minimally invasive diagnostic procedure for AR-PCNSL appears feasible. The combination of positive EBV PCR in the CSF and positive SPECT thallium has been shown to have 100% positive predictive value for lymphoma in AIDS patients with cerebral mass lesions. Likewise, if both tests are negative, the negative predictive value for lymphoma is 100%. Discordant findings require biopsy or persistent growth in the presence of anti-toxoplasmosis therapy in order for an empiric lymphoma diagnosis to be made. While minimally invasive approaches to defining focal brain lesions has gained acceptance and is considered an acceptable standard of care for initiation of specific therapy in AR-PCNSL in certain settings, the use of these studies have not been studied in terms of tumor response to therapy or in the relapsed setting. Also, the peripheral blood EBV loads have not been well correlated with AR-PCNSL, though there is evidence that the peripheral EBV load is

elevated in the setting of AR-PCNSL. Thus, study of EBV in the spinal fluid and plasma before, during and after treatment may provide preliminary information that can be useful for developing additional measures to assess tumor response (e.g. relatively non-invasive measures of minimal residual disease) and could provide a means toward predicting durability of response. Along with the more standard response assessments utilizing MRI and FDG-PET used in brain lymphoma, serial EBV DNA quantitation by PCR of the CSF and plasma will be used to provisionally assess response in correlation with the other standard outcome measures.

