## **2 ELIGIBILITY ASSESSMENT AND ENROLLMENT**

### **2.1 ELIGIBILITY CRITERIA**

#### 2.1.1 Inclusion Criteria

2.1.1.1 Positive HIV serology (previous records acceptable)

2.1.1.2 Diagnosis of Primary Central Nervous System Lymphoma

2.1.1.3 Confirmed histopathologic diagnosis by NCI Laboratory of Pathology

2.1.1.4 If tissue diagnosis is not feasible for any reason, such as undue risk to the patient to acquire tissue diagnosis, the following will be accepted as confirmed AR-PCNSL diagnosis:

- Positive brain FDG-PET and
- EBV detected in the CSF using PCR

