## **2.2 RESEARCH ELIGIBILITY EVALUATION**

### **2.2.1 Screening Studies**

All radiographic studies and EKG must be completed within 3 weeks prior to study entry; all standard laboratory tests must be done within 72 hours prior to entry; tumor diagnostic studies and viral studies may be done at any time prior to entry)

- 2.2.1.1 History and physical examination with documentation of abnormal findings
  - 2.2.1.1.1 Evaluation of ECOG status
  - 2.2.1.1.2 Detailed history of antiretroviral therapy and assessment for potential multidrug resistant HIV
  - 2.2.1.1.3 HIV genotyping and/or phenotyping if needed to assess for HIV resistance (previous outside reports adequate if done within prior 6 months)
- 2.2.1.2 Brain Imaging Studies
  - 2.2.1.2.1 MRI scan
  - 2.2.1.2.2 FDG-PET scan
  - 2.2.1.3 Computed tomography scans of the chest abdomen and pelvis to assess for peripheral lymphoma
- 2.2.1.4 Cerebrospinal fluid studies (if previously performed on sister NIAID protocol, not necessary to repeat)
  - 2.2.1.4.1 Cytopathological examination
  - 2.2.1.4.2 Flow cytometric examination
  - 2.2.1.4.3 Measurement of cell count with differential, glucose and protein
  - 2.2.1.4.4 Quantitative EBV PCR (CC Microbiology)
  - 2.2.1.4.5 Ig PCR and EBV PCR (Molecular Pathology, [name], 2N116-A)
- 2.2.1.5 Brain Biopsy at site of tumor
  - 2.2.1.5.1 May be omitted if unsafe and if FDG-PET and EBV studies are positive
- 2.2.1.6 Serum creatinine
  - 2.2.1.6.1 Calculated and/or measured creatinine clearance
- 2.2.1.7 Complete blood count and differential
- 2.2.1.8 PT and PTT
- 2.2.1.9 Biochemical assessment
  - 2.2.1.9.1 Serum electrolytes

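### The response rules ignore the baseline FDG-PET: a biopsy-proven patient who is PET-negative throughout, off steroids and cytology-negative, with an unchanged MRI lesion, fits only CRu and later CR

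*Combined protocol and SAP*

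**What the plan says.** **Entry.** Section 2.1.1.3 asks for "Confirmed histopathologic diagnosis by NCI Laboratory of Pathology" and attaches no PET result to it. Section 2.1.1.4 opens a second route, "If tissue diagnosis is not feasible for any reason, such as undue risk to the patient to acquire tissue diagnosis", and only there must the brain FDG-PET be positive and EBV be found in the CSF. Section 2.2.1.5.1 says of the biopsy: "May be omitted if unsafe and if FDG-PET and EBV studies are positive". No exclusion criterion concerns PET. FDG-PET is listed at screening (2.2.1.2.2), and section 3.8.4.2 governs only its timing: "FDG-PET: not necessary to repeat if previously done within 3 weeks of study entry".

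**Response.** Section 5.3.2 defines CRu as "either a CRu, PR or SD by MRI criteria with a completely negative FDG-PET off steroids, and negative CSF cytology" and adds: "If there is no evidence of progression while off steroids for 4 months, response will be reclassified as CR". Stable disease (SD, 5.3.5) is "not meeting the criteria for complete response, partial response, or progressive disease and with a positive FDG-PET". Partial response by volume (PR, 5.3.3.1) needs shrinkage of more than half and also a positive PET. None of these rules mentions the baseline scan.

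**Use of the categories.** The complete response rate and disease-free survival are secondary objectives (1.1.2.2). SD counts as treatment failure (5.3.6). Response category also enters sections 3.2, 3.6.3.1, 3.8.5.3.3 and 3.10.1.

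**The concern.** Treating a negative PET as evidence that a residual MRI abnormality is no longer active tumour makes sense when PET was positive before treatment and has since turned negative. Section 5.3.2 does not ask for that change; it asks only that the later scan be negative. If the scan was negative at entry, the condition is met before any drug is given and carries no information about response.

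The same wording removes the categories that would otherwise apply. Requiring a positive PET for SD and for PR by volume means that a patient who never had one cannot be placed in either while PET stays negative. What is at stake is the complete response rate, and disease-free survival if that is counted from CR. The plan does not define disease-free survival.

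**Working it through.** The plan's only design figure is the 88% power in section 6.1.3, and it reproduces. With 15 patients, the smallest success count with exact one-sided alpha at or below 0.10 against 30% is 8 (alpha 0.0500; 7 would give 0.131). Power at 65% is then 0.887. This point does not change that calculation. The check that matters is a logical one.

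**Step 1: can the patient enter?** Yes. Histology suffices under 2.1.1.3, and a negative PET only rules out the no-tissue route.

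**Step 2: which category fits?** Take a patient who is PET-negative at baseline and throughout, off steroids, cytology-negative and not neurologically worse, with an unchanged enhancing lesion.

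- CR (5.3.1): no, because the lesion is still there.
- PR by volume (5.3.3.1): no, because there is no shrinkage and PET is not positive.
- PR by cytology (5.3.3.2): no, because MRI is not normal and cytology is negative.
- Progressive disease (5.3.4): no growth, no new lesion, no neurological decline.
- SD (5.3.5): no, because PET is not positive.
- CRu (5.3.2): yes, and then CR after four months off steroids without progression.

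CR under 5.3.1 asks for neurological improvement; the CRu route does not.

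**Step 3: variants.** If the lesion shrinks by more than half, PR by volume is still closed and the patient is again CRu. If the lesion is unchanged but the patient is on steroids or has positive cytology, CRu fails, SD still needs a positive PET, and no category fits.

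**Step 4: status at the end of cycle 6.** Induction is six cycles of two weeks: 6 × 2 = 12 weeks. The upgrade to CR takes four months, so if that period starts during treatment it cannot be complete by then. Section 3.2 calls a patient without a complete response at that point a treatment failure. Section 3.8.5.3.3 schedules PET at cycle 6 only if the best response is below CRu, and otherwise at cycle 8, which treats CRu as enough to continue. The two passages do not settle the status of CRu.

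**Step 5: size.** With the 15 evaluable patients of section 6.1.3 as denominator, k such patients who would otherwise not be CR add k/15: 1/15 = 6.7 points, 2/15 = 13.3, 3/15 = 20.0. The documents give no baseline PET-negative rate q. The table shows assumed values, with expected number 15q and chance of at least one 1 − (1 − q)^15.

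| Assumed q | Expected number | Chance of at least one |
|---|---|---|
| 2% | 0.3 | 26% |
| 5% | 0.75 | 54% |
| 10% | 1.5 | 79% |
| 20% | 3.0 | 96% |

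These figures count baseline PET-negative patients, not misclassified ones. Misclassification also needs the conditions in step 2 and four progression-free months off steroids, for which the documents give no probabilities.

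**The case against.** The strongest reply is that the gap is narrow and the endpoint minor. Section 6.1.3 calls all secondary endpoints exploratory, the frequency is unknown, and several conditions must hold together. Four months without progression off steroids, in a disease the Précis describes as usually fatal within a few months, is also not evidence of failure. All of this stands, and it limits the size of the point. It does not make the category right: the rule credits a PET finding that was already present at entry.

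A reader might also draw stronger conclusions that the documents do not support.

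- *Progression-free survival is biased.* Progression (5.3.4) has no PET condition, so moving a patient from SD to CRu does not change when progression or death is recorded.
- *Treatment failure turns into success.* SD is failure under 5.3.6, but sections 3.2 and 3.8.5.3.3 leave the status of CRu at cycle 6 unclear.
- *Such a patient has had no treatment effect.* An unchanged lesion does not show that. The rule simply asks for no evidence of an effect.
- *SD is impossible for anyone PET-negative at entry.* If PET later turns positive, SD becomes available.
- *The protocol steers PET-negative patients in through biopsy.* Tissue is the default route for everyone. The sentence "Discordant findings require biopsy or persistent growth in the presence of anti-toxoplasmosis therapy" in section 1.2.5 is background that follows a discussion of EBV PCR with SPECT thallium; it is not an entry rule for FDG-PET.
- *Pre-entry steroids explain the negative baseline scans.* Section 2.1.2.1.1 permits steroids, but nothing in the documents says they cause negative scans.

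**Conclusion.** The concern holds as a definitional fault in section 5.3. For a biopsy-proven patient meeting all the conditions in step 2, the written rules lead to CRu and then CR without any change in PET or MRI. With steroids or positive cytology and an unchanged lesion, they lead to no category.

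The direct effect is possible upward bias in the exploratory complete response rate, at 6.7 points per affected patient on a denominator of 15. Disease-free survival is affected only if it is built on CR status. The 20-point figure is an upper bound: it assumes three such patients, all meeting every condition and none otherwise CR. Any effect on the two-year primary endpoint is indirect, since that endpoint also depends on survival, recurrence and neurological function class. The design power is unchanged.

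**What to change.** For endpoint scoring:

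- Apply the PET-based CRu upgrade in 5.3.2, and the positive-PET condition in 5.3.3.1 and 5.3.5, only to patients whose baseline FDG-PET was positive.
- Score patients with a negative baseline PET on MRI, CSF cytology and neurological status.
- Report how many patients had a negative baseline PET.

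This leaves one related gap. A patient who was PET-positive at baseline and turns PET-negative, with an unchanged lesion, while on steroids or with positive cytology, still has no category; section 5.3 should name one.

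The scan is already listed at screening, so no new data are needed and the sample size stands. The cost is a possibly slightly lower complete response rate, plus an editorial check elsewhere. Sections 3.2, 3.6.3.1, 3.8.5.3.3 and 3.10.1 use response category in treatment or assessment provisions, and sections 3.2 and 3.8.5.3.3 already disagree about CRu. They must be reconciled with the revised scoring; no clinical rule is proposed here.
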